STUDY OBJECTIVES:

The primary objective of this revised protocol will be to examine the safety and efficacy of IVIG 2gm/kg (maximum dose 140g) given on day#0 & day #30 plus Rituximab 1gm given on day#15. Transplanted patients will receive additional doses of Rituximab 1gm at 3 months post-transplant if DSA levels remain or become +. OR at 6M if de novo DSA occur. All transplanted patients who remain DSA-, will not receive additional Rituximab. All transplanted patients will have a protocol biopsy at 12 months.

This trial is designed to determine if Rituximab + IVIG is an effective and safe desensitization protocol and if DSAs persisting or arising at 3M and 6M post-transplant can be effectively reduced by additional doses of Rituximab. This should be reflected in reduced rates of TG for Rituximab-treated patients. This is the PRIMARY END POINT. Secondary end points include and will be evaluated based on time line in appendix A:

- Renal allograft survival at 12M

- Reduction in anti-HLA antibodies (class I/II)
- Recipient survival at 12M
- The number of acute rejection episodes
- Rates of serious infectious complications (i.e., serious infections requiring hospitalizations and/or i.v. antibiotics)
- Adverse events, toxicity assessments
- Abnormal laboratory studies: Hematology, Chemistry, Liver Function, and research tests on study
- Clinical significant abnormalities in physical examination, vital signs, weight, ECG or Chest X-ray on study
- Serial donor-specific antibody assessments
- Pre & Post-transplant determinations of CD4+/CD25+FoxP3+CD127+ & Th17 cell populations (Cedars-Sinai Patients Only).
- Pre & Post-Transplant determinations of CD19+, CD38+, CD27+ cells (Cedars-Sinai Patients Only).
- Post-Transplant biopsy at T0 and T12M assessed by Banff Criteria.
- HACA determinations at serial intervals

PRELIMINARY DATA

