This single (or multiple)-center, Phase I/II, exploratory study will use an open label design. The revision of this protocol is attributed to the failure of the placebo controlled protocol which showed a significant increase in SAEs in the IVIG + placebo group (3 antibody-mediated rejection episodes of 5 transplanted compared with 0 ABMR episodes in the IVIG + Rituximab group, $p=0.038$). The original study was put on hold and this iteration represents a redesign of the protocol to investigate the optimal dosing of Rituximab for desensitization and for modification of DSA levels post-transplant. The trial will examine the safety and efficacy of human polyclonal IgIV 10%, when given at [2.0 gm/kgx2], + Rituximab 1gm to reduce DSA to a level that is permissive for DD transplantation in 75 subjects (adults only ages ≥ 18 yrs) who are highly-HLA sensitized and are awaiting DD kidney transplant. Once transplant offers are entertained, a donor-specific crossmatch will be performed to detect anti-HLA antibodies which are associated with acute rejection or graft loss. (These anti-HLA antibodies may result naturally or from some previous pregnancy, transfusions, or prior transplants). If acceptable crossmatches and DSA levels are seen, the patients will proceed to DD transplantation. Patients receiving transplants will receive an additional dose of IVIG at transplantation (within 10 days) and will receive additional doses of Rituximab 1g) at 3M post-transplant if they remain or develop DSAs. OR at 6M if de novo DSAs occur (Fig 5 & 6). Patients who are desensitized and not transplanted within 9 M after desensitization will have completed the study and can be treated as best judged by the participating center. The protocol is shown in Figure 4 below.

[figure not shown]

Figure 4: Study Protocol for revised IVIG + Rituximab Study.

The decision to accept a DD transplant will rest entirely with the participating transplant center.

The subjects will be followed to determine the proportion who receive a transplant within 9M of completion of the infusions. In addition we will assess the transplanted patients to determine the number who sustain a viable and functioning kidney allograft for 12 months at which time a repeat study biopsy will be performed. All subjects will be evaluated on an intent-to-treat basis. The subject accrual rate will be limited to no more than five subjects per month in the initial three months to assure safety to all subjects.

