1.0 STATISTICAL CONSIDERATIONS

1.1 IVIG + Rituximab for Desensitization

Primary Objective:

This trial is designed to determine if Rituximab + IVIG is effective in improving rates of transplantation for highly-HLA sensitized DD candidates on the UNOS waiting list over a 9M period of time after completion of treatment. Results will be compared to transplant rates in a group of age and anti-HLA antibody matched patients who remain on the UNOS wait list during the study period. This is the PRIMARY END POINT. Secondary end points include and will be evaluated based on time line in appendix A:

Transplantation rate assumptions:

- 60-65% in the IVIG + Rituximab group
- ~15% in the non-desensitized patients on UNOS wait list

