1.3 Planned Efficacy Evaluations

The efficacy end points will be evaluated after all 75 patients have been enrolled into the trial. We plan to evaluate rates of deceased donor transplantation as well as conversion rate of DSA and rates of ABMR in those transplanted. The efficacy of the proposed combination of IVIG + Rituximab will be determined by the statistical methods. These evaluations will be carried out in concert with our safety monitoring that is outlined in section 9.0. The appropriate stopping points and re-evaluation points are described there as well.

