1.3.1 Primary Efficacy Variables

The primary efficacy variable is the number of highly-HLA sensitized patients receiving a deceased donor transplant within 9 months after completion of the treatment. From our previous experience, the anticipated transplant rates for patients receiving IVIG + Rituximab desensitization is ~70% (49,112, 131). The rates for DD transplantation in non-treated patients based on sensitization levels is shown in Figure 15 below. Briefly, the rates of transplantation for all sensitized patients are <12% per year for the past decade. This indicates that desensitization

with IVIG + Rituximab is likely to benefit this high risk group who are otherwise unlikely to receive a life-saving transplant.

[figure not shown]

Figure 15: Data shown in figure 14 represent an analysis of 95,083 deceased donor transplants performed over the 10 year period 2000-2009. When analyzed by PRA status, one can see that <20% of all transplants performed are in highly-HLA sensitized patients. Data from the United States Renal Data Systems (usrds.gov) for 2009 also show that the wait time for a deceased donor kidney for patients with PRAs <10% is 4 years but increases to 8 years for patients with PRAs >10%. These trends have not changed over the past decade.

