1.3.2 Secondary Efficacy Variables

In addition to the primary efficacy variables, we will evaluate a number of secondary efficacy variables. These include donor-specific antibody testing, patient and graft survival, infectious complications, immunologic testing, protocol biopsies and rates of allograft rejection. These end points are outlined in section 2.0 and Appendix A. Data will be analyzed in the treatment group.

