1.3.3 Methods of Analysis

Rituximab + IVIG for Desensitization

We aim to recruit 75 HS patients on the basis of a clinically relevant increase in the absolute rate of transplantation for highly-HLA sensitized deceased donor recipients of approximately 50 percentage points between the two groups during 9 months of follow-up, with an estimated event rate of 15% in the control UNOS study group. We determined that this number of patients would provide the study with a power of 95%, with a two-sided type I error of 5% and a nonadherence or loss to follow up rate of 5(or 10)%. A transplant rate of 60-70% in the intervention limb is based on our experience with desensitization in the recent years (49, 113, 131). All analyses shall be performed on the basis of the intention-to-treat principle. Patients that were transplanted outside of the study will be included in the analysis.

We shall compare the proportions of patients in the treatment group compared to the UNOS control group using time-to-event analysis with respect to outcomes such as the primary outcome (rate of transplantation) and certain secondary outcomes (such as recipient and graft survival, occurrence of rejection in the treatment group only). These outcomes shall be analyzed with the use of the log-rank test. Cox proportional-hazards regression shall be used to obtain unadjusted hazard ratios and to adjust for significant stratifying variables and to test for effect modification in all secondary analyses. Data from patients who are lost to follow-up shall be regarded as censored at the time of the last contact. Data from patients who do not receive transplantation shall be censored at end of 9 months post desensitization. We shall use Kaplan–Meier estimates of the proportion of patients with the above listed outcomes. We shall calculate the number of patients who would need to be desensitized to allow one deceased donor renal transplant from the hazard ratio and its 95% confidence interval.

For other outcomes, the Chi square or Fischer exact test shall be used if the variable is categorical, and the t-test or signed rank test if it is continuous variable.

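### STUDY OBJECTIVES attaches the primary end point label to reduced transplant glomerulopathy, the statistical section makes 9-month deceased-donor transplantation primary, and the glomerulopathy claim has no comparator

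*Combined protocol and SAP*

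**What the plan says.** In STUDY OBJECTIVES, the paragraph on what the trial is designed to determine covers the efficacy and safety of desensitization, then the lowering of DSA by further rituximab, and ends: "This should be reflected in reduced rates of TG for Rituximab-treated patients. This is the PRIMARY END POINT". The 13 secondary end points that follow do not include the transplant rate. They do include the biopsies at transplant and at 12 months, which are the means of measuring TG.

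The statistical section differs:

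- **1.1** attaches the same label to the transplant rate over 9 months, compared with matched patients "who remain on the UNOS wait list during the study period. This is the PRIMARY END POINT".
- **1.3.1**: "The primary efficacy variable is the number of highly-HLA sensitized patients receiving a deceased donor transplant within 9 months after completion of the treatment".
- **1.3.3** refers to "the primary outcome (rate of transplantation" and specifies a log-rank comparison with the UNOS group.
- **1.3**: "We plan to evaluate rates of deceased donor transplantation as well as conversion rate of DSA and rates of ABMR in those transplanted". TG is not mentioned.
- **1.3.2** places among the secondary variables "immunologic testing, protocol biopsies and rates of allograft rejection", and adds: "Data will be analyzed in the treatment group".

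STUDY DESIGN agrees with the statistical section: "The subjects will be followed to determine the proportion who receive a transplant within 9M of completion of the infusions".

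**The concern.** A reader should be able to identify the primary end point from the objectives. Here the objectives and the statistical section give different answers, both in current text.

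There is a second problem. A claim that TG is reduced in rituximab-treated patients needs patients without rituximab, or a reference rate fixed in advance, and the plan appears to offer neither. Anyone who judges the trial by its STUDY OBJECTIVES would expect a TG result that the design cannot give. The outcome the trial is actually built to estimate does not appear in that section at all.

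**Working it through.** **1. Which outcome was the trial sized for?** Section 1.2 uses a normal-approximation 95% interval around a 50% transplant rate, with half-width = 1.96 × √(p(1−p)/n) and p = 0.50:

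| n | Recomputed | Stated in 1.2 |
|---|---|---|
| 60 | 0.1265 | 0.127 |
| 70 | 0.1171 | 0.117 |
| 75 | 0.1132 | 0.113 |

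At n = 75 the lower limit is 0.50 − 0.113 = 0.387, as stated. At an observed 60% the half-width is 1.96 × √(0.60 × 0.40/75) = 0.111, giving 48.9% to 71.1% against the stated 49% to 71%. The plan's figures reproduce, and they concern transplantation only. The power statement in 1.3.3 (15% in controls, about 50 percentage points more with treatment) is also about transplantation. No TG rate enters either calculation.

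**2. What does each candidate primary have behind it in the supplied text?**

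| | 9-month transplantation | TG at 12 months |
|---|---|---|
| Assumed rates | 1.1, 1.2, 1.3.3 | none |
| Sample size | 1.2, 1.3.3 | none |
| Comparator | UNOS wait-list group (1.1, 1.3.3) | none |
| Named test | log-rank (1.3.3) | at most the general chi-square or Fisher line for other outcomes (1.3.3) |
| Status in section 1 | primary | biopsies secondary (1.3.2) |

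**3. Could any group serve as the TG reference?**

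- *Within the trial:* all 75 subjects are assigned rituximab before transplant, so there is no rituximab-free transplanted group.
- *UNOS controls:* about 15% are assumed to be transplanted, but no biopsies are planned for them.
- *Re-dosed against not re-dosed patients:* the plan does not propose this. It would be confounded, because DSA triggers the extra dose.
- *Biopsy at transplant against biopsy at 12 months:* both are scheduled, but no such contrast is planned for TG.
- *Earlier IVIG + placebo recipients:* few (5 transplanted according to STUDY DESIGN, 7 according to 1.2) and not named as a TG comparator.

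**4. How precisely could TG incidence be described?** The documents give no TG rate, so 10 cases are assumed for illustration.

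- Transplanted: 75 × 0.50 = 37.5, taken as 38; 75 × 0.65 = 48.75, taken as 49.
- If 20% have no 12-month biopsy: 38 × 0.80 = 30.4, taken as 30; 49 × 0.80 = 39.2, taken as 39. The 20% is an assumption, borrowed from the 80% deceased-donor graft survival up to 24 months in the preliminary data.
- Exact (Clopper-Pearson) 95% intervals, from the beta quantiles B(0.025; x, n−x+1) and B(0.975; x+1, n−x):

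| Cases / biopsied | Proportion | 95% interval |
|---|---|---|
| 10/38 | 26% | 13.4% to 43.1% |
| 10/49 | 20% | 10.2% to 34.3% |
| 10/30 | 33% | 17.3% to 52.8% |
| 10/39 | 26% | 13.0% to 42.1% |

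Fixing 10 cases lets the proportion rise as n falls. Holding it at 20% instead, 6/30 gives 7.7% to 38.6%, against 10.2% to 34.3% for 10/49. Either way the interval spans roughly 24 to 36 percentage points and describes one treated cohort.

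**The case against.** The best reply is that the paragraph in STUDY OBJECTIVES is loosely drafted and does not set up a rival primary. The label may refer back to the whole paragraph, with TG as an expected consequence. The same section lists the biopsies as secondary, and 1.1 opens in nearly the same way before defining efficacy as the 9-month transplant rate. Every part of the statistical section fits transplantation as primary, and the study is described as exploratory. Some text (sections 2.0 and 9.0, Appendix A, Figures 4-6) is not in the supplied documents and might say more about TG.

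Much of this is fair. The broad reading is possible, and the consistency of the statistical section limits the room to choose a headline result afterwards. But the broad reading does not remove the conflict: the primary would then be a bundle of desensitization efficacy and safety, DSA reduction and TG, still without the transplant rate. The unseen text could add a TG analysis, but it would leave the label in STUDY OBJECTIVES as it stands.

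Two further points limit the illustration rather than the finding. The 20% without a biopsy comes from survival up to 24 months, while the earlier 20-patient study reported 94% graft survival at 1 year; 6% missing would give sample sizes between the two cases shown. Sections 1.3.1 and 1.3.3 also mention transplant rates up to about 70%, which would be 75 × 0.70 = 52.5, about 52 patients, and only slightly narrower intervals. It is also true that a pre-specified external TG rate could supply a reference, but the supplied text contains none.

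**Conclusion.** The concern holds and must be fixed. On either reading of the label, STUDY OBJECTIVES and sections 1.1, 1.3.1 and 1.3.3 disagree on the primary end point, and only 9-month deceased-donor transplantation is sized, compared and assigned a test. On the supplied text, the trial cannot support a claim that rituximab reduces TG. It can estimate TG incidence in transplanted patients, with exact 95% intervals of about 10-34% to 17-53% under the assumptions of 10 cases, 50-65% transplanted and 0-20% without a 12-month biopsy. The conflict between sections does not depend on those assumptions; they affect only the illustrated precision.

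**What to change.** In STUDY OBJECTIVES, name deceased-donor transplantation within 9 months of completing treatment as the single primary end point, in agreement with 1.1, 1.3.1 and 1.3.3. Make 12-month TG a secondary, descriptive outcome in transplanted patients: incidence with an exact 95% interval, plus the number without a 12-month biopsy by reason (graft loss, death, not done). Keep post-transplant DSA change as secondary, as already listed. Delete the statement that TG will be reduced in rituximab-treated patients.

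The cost is one reworded paragraph and one reporting line for missing biopsies. Biopsies and serial DSA are already scheduled, so no data collection is added. The price is that TG becomes descriptive, with wide intervals, but the opening background section already speaks of determining its incidence.

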≥ 3 Ag match	18 (24%)

Flow PRA denotes panel reactive antibody as determined by flow cytometry assays. DD denotes deceased donor. LD denotes living donor. CMV denotes cytomegalovirus. PVB 19 denotes Parvovirus B19. HLA denotes human leukocyte antigen. †= death.

Figure 1: This figure shows an analysis of transplantation and outcomes by PRA and donor type. 75% of patients had PRA >80%. There were also more ABMR episodes and graft losses to ABMR in this group.

Outcomes by PRA Status & Donor Type After Desensitization (N=76)

[figure not shown]

Table 3: Shows AR episodes and graft losses in the patients receiving transplants after desensitization. Relationship of ABMR to DSA levels at time of transplant is also shown.

Rejection Types & Graft Loss by DSA	Outcomes	Significance
Total AR Episodes	28/76 (37%)	
Total CMR Episodes (3DD / 3LD)	6/76 (8%)	
Total Graft Loss to CMR	0/76 (0%)	
Total AMR Episodes (11DD / 11LD)	22/76 (29%)	
AMR+ (DSA<100,000 SFI Units)*	5	
AMR- (DSA<100,000 SFI Units)	42	
AMR+ (DSA >100,000 SFI Units)*	17	**P<0.0000004
AMR- (DSA >100,000 SFI Units)	12	
Graft Loss to AMR by DSA <100,000 SFI Units	2/5*** (40%)	
Graft Loss to AMR by DSA >100,000 SFI Units	5/17*** (29%)	P=NS

*DSA values obtained at time of transplant

**Statistics is by χ^2 analysis

***This data includes 2 patients with late AMR due to non-compliance 12 months post-transplant.

Figure 2A & B: This figure shows T-cell FCMX values for pre-treatment and at time of transplant for 31 HS LD (2A) and 45 HS DD (2B) recipients who were desensitized with IVIG+ rituximab. A negative T-cell FCMX is <50 MCS.

Figure 2A

[figure not shown]

Figure 2B

[figure not shown]

Figure 3A & B: This figure shows non-death censored patient and graft survival values at 0M, 1M, 6M, 12M and 24M for 76 HS patients who were desensitized with IVIG + rituximab. (3A) Patient and Graft Survival for all patients up to 24M post transplant. (3B) Patient and Graft Survival by donor type LD (N=31) and DD (N=45) for the same period.

Figure 3A

[figure not shown]
[figure not shown]

Figure 3B

STUDY DESIGN:

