Figure 5: Pre-Transplant Desensitization Protocol for deceased donor recipients:

[figure not shown]
[figure not shown]

Figure 6 Shows the Post-Transplant Management Protocol for Patients Receiving DD Transplants.

ACCRUAL GOAL: 75 subjects

DURATION OF ACCRUAL: 24 months

DURATION OF FOLLOW-UP: 9 months for all desensitized subjects, 12 months for all transplanted subjects

THERAPY STOPPING RULES: Safety stopping rules for the study include:

The study will be put on hold and re-evaluated for safety signals if significant adverse events (serious infusion reactions, serious infections or death and or graft loss from early ABMR) are seen in three of the first 5 patients. In addition, if biopsy proven ABMR is seen in 4 of the first 10 patients entered, the study will be stopped for re-evaluation.

Efficacy Stopping Rules:

The DSMB will review cumulative safety and efficacy data according to a pre-specified schedule, not less frequently than quarterly. Based on these data (after the pre-specified data reviews, the DSMB may recommend alterations or stopping of the protocol.

CONCOMITANT MEDICATIONS: Concomitant therapy will include a standard immunosuppressive regimen of mycophenolate mofetil (CellCept[®]) at 1200 mg/m²/day given in two divided doses, Tacrolimus (Prograf[®]) given at 0.05 to 0.15 mg/kg divided twice daily, and prednisone loading dose and taper as per center protocol. Induction therapy using Campath 1H 30mg SQ/IV at the time of transplant OR Thymoglobulin[®] (total dose not to exceed 6.0mg/kg) IV per center protocol will be given to subjects on study. The safety and efficacy of Campath 1H induction therapy after desensitization with IVIG + Rituximab has been previously described for adults (11,12).

Therapy for recurrent biopsy proven rejection will be initiated as standard of care at participating institutions. The recommended initial rejection therapy will consist of pulse Solumedrol per center protocol. Alternatively, Thymoglobulin will typically be given for 5-10 days, depending on the time of return of creatinine levels to baseline. If resistant ABMR is seen, the use of IVIG +Rituximab (anti-CD20 monoclonal antibody) and/or plasmapheresis will be considered. In addition, the use of monoclonal antibodies to the complement component C5 (Eculizumab[®], Alexion, Cheshire, CT) may be used at the discretion of the investigators.

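### The ABMR stopping rule counts patients entered, not patients transplanted, so its chance of triggering depends on the transplant rate

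*Combined protocol and SAP*

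**What the plan says.** Under THERAPY STOPPING RULES the protocol gives two triggers. The first puts the study on hold if three of the first 5 patients have a significant adverse event. That list covers serious infusion reactions and serious infections, and it brings in ABMR through "death and or graft loss from early ABMR". The second stops the study for re-evaluation "if biopsy proven ABMR is seen in 4 of the first 10 patients entered".

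Under STUDY DESIGN, patients are desensitized first and go on to transplant only if crossmatch and donor-specific antibody (DSA) levels are acceptable. Those not transplanted within 9 months have completed the study. On acceptance of an organ it says: "The decision to accept a DD transplant will rest entirely with the participating transplant center".

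Elsewhere ABMR is reported per transplanted patient. SAP section 1.3 plans to evaluate "rates of ABMR in those transplanted". STUDY DESIGN describes the earlier placebo-controlled phase as having "3 antibody-mediated rejection episodes of 5 transplanted" in the IVIG + placebo group. Table 3 of the preliminary data uses 76 transplanted patients.

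The assumed transplant rate is "60-65% in the IVIG + Rituximab group" in SAP section 1.1, at least 50% in section 1.2, and about 70% in section 1.3.1. The documents give no operating characteristics for either rule.

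**The concern.** Entry comes before desensitization, and a sizeable share of entrants are expected never to receive a graft. Each of them uses up one of the ten places without being at risk of the event. The window is also fixed by order of entry, so ABMR in the eleventh or twelfth entrant is ignored even if that patient was transplanted before some of the first ten.

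The rule therefore becomes less sensitive as fewer patients are transplanted, although the harm it watches for concerns only those who are. Nothing in the documents suggests that this link was intended. ABMR is also the event behind the hold on the earlier phase, so a pre-specified trigger for it should behave predictably.

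The 3-of-5 rule does not fill the gap. It names ABMR only when death or graft loss follows, and in Table 3 only 7 of the 22 ABMR cases (2 + 5) lost the graft.

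**Working it through.** The plan states no error rate for this rule, so there is no figure of its own to reproduce.

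**Inputs**
- Transplant rate t: 50% (SAP 1.2), 60% and 65% (SAP 1.1), 70% (SAP 1.3.1), and 13/15 = 87% (the placebo-controlled phase, SAP 1.2).
- Background ABMR rate per transplanted patient: 11/45 = 24% for deceased-donor recipients (Table 3, row "Total AMR Episodes (11DD / 11LD") and 22/76 = 29% overall.
- Illustrative high rate a = 60%. This is the 3/5 in the earlier IVIG + placebo group. It is close to 17/(17 + 12) = 59% in Table 3 for recipients with DSA above 100,000 SFI (row "AMR+ (DSA >100,000 SFI Units").
- Patients are assumed independent.

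**Current rule.** Each entrant has ABMR with probability t × a, so P(trigger) = P(Bin(10, t × a) ≥ 4). At t = 0.60 and a = 0.60 this is P(Bin(10, 0.36) ≥ 4) = 0.513. The share of expected grafts that must have ABMR is 4/(10t). The rule cannot trigger at all if fewer than 4 of the 10 are transplanted.

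| Transplant rate | Share of grafts needed | P(fewer than 4 grafts) | Trigger at 60% ABMR | False hold at 24-29% |
|---|---|---|---|---|
| 50% | 80% | 17% | 35% | 3-4% |
| 60% | 67% | 5% | 51% | 5-8% |
| 65% | 62% | 3% | 59% | 6-10% |
| 70% | 57% | 1% | 67% | 8-13% |
| 87% | 46% | <0.1% | 86% | 14-23% |

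**How much is due to the denominator?** With exactly 6 grafts, P(Bin(6, 0.60) ≥ 4) = 0.544, against 0.513 for 10 entered at 60% transplanted. At a fixed transplant rate the wording costs about 3 points. The rest of the weakness is the small number of grafts, and the wording makes that number depend on t.

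**Rules based on transplanted patients.** P(trigger) = P(Bin(n, a) ≥ k), which does not involve t.

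| Rule | a = 24% | a = 29% | a = 60% |
|---|---|---|---|
| 4 of first 7 transplanted | 7% | 11% | 71% |
| 5 of first 10 transplanted | 7% | 13% | 83% |
| 4 of first 10 transplanted | 21% | 32% | 95% |

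Changing only the word and leaving 4 of 10 would give too many false holds, so n or k must also move. At ABMR rates of 40% and 50%, 4 of 7 triggers 29% and 50% of the time, against 20% and 35% for the current rule at 60% transplanted.

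**Timing.** A simulation of 15,000 runs per setting used assumptions that are not in the plan: entry spread evenly (75/24 = 3.125 a month), one month of treatment, a uniform wait of 0-8.4 months (mean 4.2) or 5-9 months (mean 7), ABMR one month after transplant, and a = 60%. Among runs where the current rule triggers, 4 of 7 was later or never triggered in about 5% to 16% for transplant rates of 50-70%. All of these were runs in which it never triggered: with a constant lag to ABMR, it cannot come later if it triggers at all. For 5 of 10 transplanted the figure was about one third with the short wait and about 70% with the longer one.

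**The case against.** The strongest counter-argument is that the problem is sample size, not wording. Keeping entered patients but using 5 of the first 17 would detect 60% ABMR 79% of the time at 60% transplanted, with 9-16% false holds. This largely stands. A reader might infer that the word alone explains a gap such as 51% against 83%. It does not: most of that gap comes from observing ten grafts instead of about six. What survives is that the current rule's behavior shifts with the transplant rate, and a rule on transplanted patients does not.

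A reader might also infer that 60% is the plan's unacceptable rate, or a likely rate here. The documents do not support that. The 3/5 came from IVIG + placebo, and the rituximab group had no ABMR. SAP section 1.2 counts 7 transplanted in that placebo arm, which would make it 3/7 = 43%. The 17/29 is the high-DSA stratum; the low-DSA stratum had 5/(5 + 42) = 11%. The 60% is illustrative only. Nor does it show much that three cases could not meet a four-case rule, because the earlier hold rested on a between-arm comparison.

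Finally, a reader might conclude that nothing else protects patients. The DSMB reviews cumulative data at least quarterly and may recommend stopping, and safety data are reported to centers and the funder with each occurrence. SAP section 1.3 refers to stopping points in a section 9.0 that is not in the supplied text. These backstops count, but the review as described is discretionary with no ABMR threshold, and none of them changes what this sentence counts.

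**Conclusion.** The point holds as a cheap improvement to a safety rule, not as a flaw that invalidates the trial. The denominator includes patients who cannot have the event and leaves out some who can. Over the plan's own 50-70% transplant rates, the chance of triggering at 60% ABMR ranges from 35% to 67%, mainly because only five to seven grafts are expected. The figures rest on independence between patients and on the illustrative 60%. The 24-29% background comes from the earlier series, in which all patients were transplanted after the same desensitization doses. The timing results rest on assumptions about accrual, waiting time and ABMR onset. Whether section 9.0 restates the rule cannot be checked.

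**What to change.** Replace the sentence with: *If biopsy-proven ABMR within 12 months after transplant is seen in 4 of the first 7 patients transplanted, counted in order of transplant, the study stops for re-evaluation.* The rule acts as soon as the fourth case occurs. The 12 months match the existing follow-up of transplanted patients. If section 9.0 repeats the rule, change it there too. In the same paragraph, say whether the first 5 patients in the other rule are those entered, treated or transplanted.

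The cost is one sentence and no new procedures, since transplant dates and rejection are already needed for the endpoints. False holds become 7-11% at any transplant rate. That is higher than now at 50% transplanted (3-4%) and 60% (5-8%), about the same at 70% (8-13%), and lower at 87% (14-23%). If the true background were 35%, false holds at 60% transplanted would rise from 14% to 20%. Detection of 60% ABMR would be 71%, which is better than now at 50-70% transplanted but worse than the current 86% at 87%.

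The sponsor may prefer 5 of the first 10 transplanted (83% detection, 7-13% false holds), accepting that it often acts later than the current rule. The threshold is a judgment; the denominator should be transplanted patients.
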